## **5.2 Tumor Collection**

Following registration, patients will undergo collection of multiple myeloma cells through bone marrow aspirate collection. Bone marrow aspirates will be obtained (20-30cc) under local anesthesia. If there is an insufficient yield of tumor cells a second collection will be permitted.

At the time of tumor collection, 50ml of plasma in sodium heparin tubes will be collected from the peripheral blood. This will be repeated if a second collection is indicated. Standard infectious serologies will be drawn as per BIDMC practice for storage of cellular products (drawn in 2 red top tubes and 3 pink top tubes and sent to the Stem Cell Lab at BIDMC).

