13. EKG
14. Skeletal bone survey or alternative imaging to include cranium, axial skeleton and proximal long bones or alternative imaging to capture areas of bone disease, if clinically indicated
15. Evaluation of Pre-Treatment Eligibility Criteria and registration to second time point on study.

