## 6.1 Dose Delays

To initiate cycle 1 of therapy with vaccine and nivolumab, participants must meet the eligibility criteria outlined in section 3.3.

Patients experiencing any of the following toxicities judged to be possibly or definitely related to study treatment will not receive further therapy.

- Grade 3 or higher non-hematologic toxicities that do not resolve within 14 days of onset;
  - Please note the following exceptions indicated in Appendix B that necessitate immediate discontinuation of therapy:
    - Grade 4 creatinine elevation
    - Grade 3 or higher pulmonary toxicity
    - ALT/AST or total bilirubin grade 3 or higher elevation
    - Grade 3 or higher adrenal insufficiency
    - Grade 3 or higher neurological adverse event
    - Grade 3 or higher myocarditis
- Grade 4 or higher non-hematologic toxicities;
- Grade 4 or higher hematologic toxicities that do not resolved within 7 days of onset;
  - Please note that this excludes lymphopenia, as mentioned in section 5.9.3;
- Grade 4 or higher nivolumab infusion reactions.
- Laboratory abnormalities that are not thought to be clinically significant (i.e. lymphopenia) will not be included in criteria for holding of therapy

Patients experiencing grade 3 non-hematologic toxicity, grade 2 immune associated toxicity as outlined in Appendix B, and grade 4 hematologic toxicity will have therapy held.

Patients not meeting these criteria may have therapy held for clinical reasons with the approval of the study PI or designee.

Patients who experience grade 4 hematologic toxicity that resolves to grade 1 or baseline within 7 days OR grade 3 non-hematologic toxicity that resolves to grade 0-1 within 14 days OR grade 2 immune associated toxicity requiring hold of therapy as outlined in Appendix B that resolves to grade 0-1 within 14 days may have therapy restarted UNLESS otherwise specified in Appendix B.

Therapy is restarted at the point of dose interruption so that all intended doses of vaccine and nivolumab are administered.

Patients experiencing recurrence grade 3 non-hematologic toxicity, grade 2 immune associated toxicity as outlined in Appendix B, and grade 4 hematologic toxicity will have therapy discontinued UNLESS otherwise specified in Appendix B.

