### **7. IDENTIFICATION OF TREATMENT LIMITING TOXICITIES**

Treatment limiting toxicities (TLT) will be defined as toxicity judged to be possibly or definitely related to the study treatment and meeting the following criteria:

- Grade 3 or higher non-hematologic toxicities that do not resolve within 14 days of onset;
  - Please note the following exceptions that necessitate immediate discontinuation of therapy:
    - Grade 4 creatinine elevation
    - Grade 3 or higher pulmonary toxicity
    - Grade 3 or higher ALT, AST or total bilirubin elevation
    - Grade 3 or higher adrenal insufficiency
    - Grade 3 or higher neurological adverse event
    - Grade 3 or higher myocarditis
- Grade 4 or higher clinically significant non-hematologic toxicities;
- Grade 4 or higher hematologic toxicities that do not resolve to grade 1 or baseline within 7 days of onset;
  - Please note that this excludes lymphopenia, as mentioned in section 5.9.3;
- Grade 4 or higher nivolumab infusion reactions.

Patients experiencing TLT will not receive further therapy

If 3 or more patients experience a TLT within the first 28 days of initiating therapy among the first 10 patients enrolled, then accrual will be suspended. TLTs will be defined per the above criteria with grades determined by CTCAE version 4.0 that are possibly, probably or definitely related to the study treatment. Patients will be monitored for the occurrence of TLTs during the first 28 days of treatment.

Once the 10th participant is enrolled, accrual will be paused until the 10th participant completes a full cycle of treatment (28 days) without experiencing any TLTs.

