As a secondary clinical endpoint, response will be assessed according to IMWG response criteria. In a prior phase I trial of DC/MM vaccination in patients with relapsed MM, 69% (11/16) patients had disease stabilization. No patients demonstrated disease response (PR, VGPR, or CR). In the present phase II trial, overall response rate per IMWG criteria will be assessed. An exact binomial test with a 10% one-sided significance level will have 82% power to detect the difference between the ORR proportion of 0.15 (null hypothesis) and the alternative ORR proportion of 0.35 when the sample size is 25. An ORR of 35% is considered worthy of further study in a larger trial.

If 3 or more patients experience a TLT, accrual will be suspended.

	True but Unknown Rate of DLT				
	0.10	0.20	0.25	0.30	0.40
Probability of continuation of enrollment ( $\leq 2$ TLT in 10 pts)	0.930	0.678	0.526	0.383	0.167

If the true rate of TLT is 25%, the probability of observing 2 or fewer TLTs within a cohort of 10 patients is 0.526.

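### The toxicity rule suspends accrual, which happens at registration; as written, patients already registered but still in vaccine production may start the combination after the third treatment limiting toxicity

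*Combined protocol and SAP*

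**What the plan says.** Section 7 is triggered as follows: "If 3 or more patients experience a TLT within the first 28 days of initiating therapy among the first 10 patients enrolled". The same sentence ends with the action: "among the first 10 patients enrolled, then accrual will be suspended". Section 14.1 restates the consequence without the window: "If 3 or more patients experience a TLT, accrual will be suspended". Neither section says anything about first doses. The other stop in section 7 concerns the affected patient alone: "Patients experiencing TLT will not receive further therapy".

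The order of events is set elsewhere. Section 4.1 requires registration before any protocol intervention. Section 5.2 then begins: "Following registration, patients will undergo collection of multiple myeloma cells through bone marrow aspirate collection". Leukapheresis, dendritic cell culture and bridging follow.

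Before treatment, section 5.5 item 15 lists "Evaluation of Pre-Treatment Eligibility Criteria and registration to second time point on study", and section 6.1 states: "To initiate cycle 1 of therapy with vaccine and nivolumab, participants must meet the eligibility criteria outlined in section 3.3". The section 3.3 criteria are resolution of chemotherapy toxicity, vaccine yield, no progression, performance status, organ function and washout. All of them concern the individual patient.

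**The concern.** This is the only numeric safety boundary in the plan, and its purpose is to limit exposure to a combination that proves too toxic. In most trials accrual and first dose are days apart, so stopping one stops the other. Here they are separated by vaccine manufacture and bridging. A site that follows the text exactly could close new registrations after the third TLT and still take an enrolled, untreated patient through the second registration to a first combined dose. The plan requires no DSMC review between the two. The suspension therefore acts on a step that comes before the one where exposure begins.

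**Working it through.** **1. The plan's own figure.** The probability of continuing is P(X ≤ 2) with X ~ Binomial(10, p). At p = 0.10, 0.20, 0.25, 0.30 and 0.40 this gives 0.9298, 0.6778, 0.5256, 0.3828 and 0.1673, which matches the table in section 14.1. The rule fires with the complement: 0.070, 0.322, 0.474, 0.617 and 0.833.

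**2. The lag from registration to first dose.**
- Dendritic cell culture (section 9.2.2): 5–7 days plus 48–72 hours, so 7–10 days.
- Bridging: 1–2 cycles during vaccine generation (section 1.1), with up to 1 cycle before leukapheresis (5.3) and up to 2 after it (5.4).
- Cycle length and accrual rate are not given, so the lag is certainly weeks but its exact length is an assumption.

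**3. What accrual means.** Section 7 also pauses accrual at the 10th enrolment until that "participant completes a full cycle of treatment (28 days) without experiencing any TLTs". If accrual included the start of immunotherapy, the 10th participant could not start and the pause could never end. Within section 7, accrual therefore means enrolment.

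**4. Ceiling.** The third TLT needs at least 3 dosed patients. With enrolment paused at 10, at most 10 − 3 = 7 are still undosed. The cap could fail if the 10th participant finishes 28 days while an earlier enrolee is still in production, because accrual then reopens.

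**5. Upper bound on the mean.** Suppose all 10 are registered, dosing is one at a time and each outcome is known before the next start. The third TLT falls in the k-th dosed patient with probability C(k−1, 2) p³(1−p)^(k−3), leaving 10 − k. Given that the rule fires:

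| True TLT rate | Mean still to start | Further expected TLTs (mean × rate) |
|---|---|---|
| 25% | 2.75 | 0.69 |
| 30% | 3.03 | 0.91 |
| 40% | 3.66 | 1.46 |

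**6. Under assumed accrual and lag.** This is a simulation with Poisson arrivals, lag uniform over 28–70 days and TLT onset uniform over the 28 days after first dose. It counts patients registered but undosed at the third TLT, given that the rule fires. Each cell shows the mean, then the share of such trials with at least one waiting:

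| True TLT rate | 0.5 per 28 days | 1 per 28 days | 2 per 28 days |
|---|---|---|---|
| 25% | 0.64 (47%) | 1.10 (64%) | 1.55 (69%) |
| 30% | 0.67 (49%) | 1.18 (67%) | 1.70 (73%) |
| 40% | 0.74 (53%) | 1.34 (73%) | 2.04 (81%) |

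Over the same accrual and TLT rates, other lags give:
- 28–56 days: 0.56 to 1.85 (43–79%).
- 30–76 days: 0.69 to 2.14 (49–82%).
- 28–84 days: 0.73 to 2.21 (51–83%).

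In summary, for a lag of about 1 to 2.5 months the mean is about 0.6 to 2.1, with at least one patient waiting in roughly 40 to 80% of trials in which the rule fires. No attrition is modelled.

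**The case against.** The documents are silent here, not contradictory, and that silence does not oblige anyone to dose. Section 6.1 makes the section 3.3 criteria necessary. It does not say that they are sufficient. The DSMC receives TLT information and raises safety questions with the Overall PI (section 13.2), and life-threatening complications reach the Overall PI at once (section 8.3.1). A site might also treat the second registration as part of accrual. All of this could stop a first dose in practice, but none of it is written into the rule. DSMC review is up to four times a year and is not triggered by the third TLT. The accrual reading is hard to square with the pause at the 10th enrolment.

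Attrition stands as an objection to the size. Waiting patients must still yield at least two vaccines and not progress (section 3.3), and those who progress before treatment leave the study (section 5.15). The counts above are therefore high.

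A reader might infer that three to four patients will typically be exposed after the boundary. The documents do not support that. It needs all 10 registered at the outset and one-at-a-time dosing, and no such staggering is stated. A reader might also infer that the suspension protects nobody in the first 10. It does spare any of them not yet registered.

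**Conclusion.** The gap holds on the text and needs no assumption: the stated action stops registration, exposure begins weeks later, and nothing links the two. Its size does rest on assumptions. With 0.5 to 2 patients per 28 days, a lag of about 1 to 2.5 months and TLT rates of 25 to 40%, an average of about 0.6 to 2.1 patients are registered but undosed when the rule fires, normally no more than 7, before loss to failed production or progression. The means of 2.75 to 3.7 are an upper bound and should not be read as the expected number. This is a flaw in the scope of a safety rule that is worth correcting. The continuation table is right as it stands.

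One related conflict bears on when exposure starts. Section 14.1 has patients receiving nivolumab during vaccine production, whereas sections 1.1, 5 and 5.4 describe standard-of-care bridging. These passages must be reconciled, because they also fix the start of the 28-day TLT window.

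**What to change.** Reconcile sections 7 and 14.1 with sections 3.3, 5.5 and 6.1 so that the suspension is defined in relation to the step at which exposure begins, the second-time-point registration. The text should state how it applies to patients enrolled but not yet treated, and that the DSMC reviews the TLTs before it is lifted. The clinical handling of waiting patients is for the sponsor, the investigator and the DSMC to decide.

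The cost is a few sentences, using a registration step and a committee that already exist, and the probabilities in section 14.1 do not change. The downside is that, if the suspension reaches them, patients with a frozen vaccine may wait during a review and some may progress. This would also happen when the combination is tolerable: the rule fires 1 − 0.930 = 7% of the time at a true TLT rate of 10%, and 1 − 0.678 = 32% at 20%.

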### **5.12 Agent Administration**

#### **5.12.1 Nivolumab**

Patients will be treated with Nivolumab 240 mg on days 1 and 15 of a 28-day cycle. Nivolumab will be given every two weeks ( $\pm 3$  days). Patients may be dosed no less than 12 days from the previous dose of drug.

Nivolumab is to be administered as a 60-minute IV infusion (+/- 10 minutes), using a volumetric pump with a 0.2/1.2 micron in-line filter at the protocol-specified dose. The drug can be diluted with 0.9% normal saline for delivery but the total drug concentration of the solution cannot be below 1.0 mg/mL. It is not to be administered as an IV push or bolus injection.

Vital signs (BP, HR, Temp, RR, O2 sat) will be taken within 15 minutes prior to start of nivolumab infusion and within 15 minutes following completion of the infusion.

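### Duration-based TLTs that start late in cycle 1 cannot be classified by day 28, when the accrual pause ends, and section 7 does not say whether a TLT is dated by onset or by the day its criterion is met

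*Combined protocol and SAP*

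**What the plan says.** Section 7 sets a group-level rule. Accrual is suspended "If 3 or more patients experience a TLT within the first 28 days of initiating therapy among the first 10 patients enrolled". The observation period has the same length: "Patients will be monitored for the occurrence of TLTs during the first 28 days of treatment". Accrual also pauses at the 10th enrollment until that "participant completes a full cycle of treatment (28 days) without experiencing any TLTs".

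The same section defines the TLTs. Two criteria depend on duration:

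- "Grade 3 or higher non-hematologic toxicities that do not resolve within 14 days of onset"
- "Grade 4 or higher hematologic toxicities that do not resolve to grade 1 or baseline within 7 days of onset"

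The others do not. A sub-list under the first criterion is introduced by "Please note the following exceptions that necessitate immediate discontinuation of therapy". It covers grade 4 creatinine elevation and grade 3 or higher pulmonary, hepatic-laboratory, adrenal, neurological and myocarditis events. Clinically significant grade 4 non-hematologic toxicity and grade 4 infusion reactions also carry no waiting period.

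Section 5.12.1 fixes the dosing inside the window: "Patients will be treated with Nivolumab 240 mg on days 1 and 15 of a 28-day cycle".

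Section 14.1 repeats the three-TLT suspension rule with no time window. Its table, in the row "Probability of continuation of enrollment", gives 0.930, 0.678, 0.526, 0.383 and 0.167 for true rates of 0.10, 0.20, 0.25, 0.30 and 0.40.

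**The concern.** The window and the definitions do not fit together. A criterion that needs 14 days after onset cannot be met inside a 28-day window unless the event starts in its first half. Section 7 does not say whether a patient has experienced a TLT on the day the toxicity begins or on the day the clock runs out. It also sets no follow-up beyond day 28 for counting purposes.

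The affected class is not empty. The immediate-discontinuation list omits gastrointestinal and skin toxicity, fatigue and hyperglycemia. Section 8.1.1.1 lists fatigue and diarrhea as very common with nivolumab, and colitis, rash and hyperglycemia as common. Those frequencies are not broken down by grade, so they do not show how many such events would reach grade 3 and persist.

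This is the only toxicity rule in the plan with a numerical threshold for accrual. It is meant to test a full cycle of vaccine plus two nivolumab doses. For persistent grade 3 toxicity outside the list, it can settle by day 28 only events that start at about the time of the second dose or earlier.

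**Working it through.** **1. Reproduce the table.** With X ~ Binomial(10, p), P(X ≤ 2) is 0.9298, 0.6778, 0.5256, 0.3828 and 0.1673 at p = 0.10, 0.20, 0.25, 0.30 and 0.40. All five tabled values are reproduced.

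**2. Dates.** The classification day is the onset day plus the clock.

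| Criterion | Clock | Last onset classifiable by day 28 | Late onsets | Classified on |
|---|---|---|---|---|
| Grade 3 non-hematologic, not on the exception list | 14 days | day 14 | days 15-28 | days 29-42 |
| Grade 4 hematologic | 7 days | day 21 | days 22-28 | days 29-35 |

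**3. Assumptions for an illustration.** The documents give neither the mix of TLT types nor the timing of onset. Let g be the share of TLTs that are the 14-day type, and take g = 0.5. Take onset as uniform over 28 days, so 14/28 of that type start too late. The hematologic gap is left out. The rate that can be seen by day 28 is

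q = p × (1 − g × 14/28) = 0.75p,

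which is 0.1875 at p = 0.25 and 0.30 at p = 0.40.

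**4. Reading A: a TLT is dated when its criterion is met.** Late-onset events never count, for any of the 10 patients. P(continue) = P(Binomial(10, q) ≤ 2).

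- p = 0.25: 0.715, against 0.526
- p = 0.40: 0.383, against 0.167
- For g from 0.25 to 0.75 (q = 0.875p to 0.625p), the value at p = 0.40 runs from 0.262 to 0.526.
- At the ceiling g = 1 (q = 0.5p), it is 0.880 at p = 0.25 and 0.678 at p = 0.40.

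**5. Reading B: a TLT is dated by onset.** Late-onset events do count, but may still be open when the pause ends. Only patients with recent starts are affected: m patients have rate q and 10 − m have rate p.

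For m = 1 (the 10th patient only), P(continue) = P(B9 ≤ 2)(1 − q) + P(B9 ≤ 1)q, where B9 ~ Binomial(9, p).

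- p = 0.25: 0.6007 × 0.8125 + 0.3003 × 0.1875 = 0.544
- p = 0.40: 0.2318 × 0.70 + 0.0705 × 0.30 = 0.183

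For m = 3 (all three starting therapy at about the same time), P(continue) = Σ P(B3 = j) P(B7 ≤ 2 − j) over j = 0, 1, 2, where B3 ~ Binomial(3, q) and B7 ~ Binomial(7, p).

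- p = 0.25: 0.5364 × 0.7564 + 0.3713 × 0.4449 + 0.0857 × 0.1335 = 0.582
- p = 0.40: 0.343 × 0.4199 + 0.441 × 0.1586 + 0.189 × 0.0280 = 0.219

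| True TLT rate | Table in 14.1 | Reading A | Reading B, m = 1 | Reading B, m = 3 |
|---|---|---|---|---|
| 0.25 | 0.526 | 0.715 | 0.544 | 0.582 |
| 0.40 | 0.167 | 0.383 | 0.183 | 0.219 |

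The value of m depends on how patient starts are staggered, which the documents do not give. Enrollment precedes vaccine manufacture and bridging therapy, so several of the first 10 could be in cycle 1 together.

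**The case against.** The strongest reply is that nothing is shown to be lost. Section 7 can be read by onset date, and the section 14.1 sentence has no window, so a TLT confirmed on day 35 would still count. Under that reading the distortion is small: 0.544 against 0.526 at a true rate of 0.25 if only the 10th patient is affected. This stands as a limit on size. It does not close the gap, because the pause can still lift while events are open, and the two sections still differ.

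A reader might infer three stronger things that the documents do not support.

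- *That all grade 3 toxicity after the second dose escapes the check.* It does not. The listed exceptions call for immediate discontinuation, and clinically significant grade 4 non-hematologic events have no waiting period. Section 5.12.1 also allows ±3 days with at least 12 days between doses, so the second dose can fall on day 13. A 14-day-type event starting on day 13 or 14 can then still be classified by day 28.
- *That TLTs are certainly undercounted.* That holds only under Reading A, and section 7 does not choose a reading.
- *That the 14.1 table is wrong.* It is arithmetically correct for whatever TLT rate the rule can observe. The open question is whether that rate includes late-onset, duration-based events.

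It can also be said that individuals are protected by the holding and discontinuation rules in section 6.1, by the TLT check before cycles 2-6, and by DSMC review (section 13.2). That is true, but none of these adds an event to the 10-patient count, and section 13.2 states no TLT threshold.

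**Conclusion.** The point holds in a limited form. As written, the 28-day window and pause cannot classify 14-day-type grade 3 non-hematologic events with onset on days 15-28, or grade 4 hematologic events with onset on days 22-28. The consequence depends on a dating rule that the plan leaves unstated. Either the events never count, or accrual can resume before they are known. Both weaken the early safety check, the second much less than the first.

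The date arithmetic needs no assumption. The probabilities do: they rest on the 50% share, uniform onset and, for Reading B, the number of patients who overlap. They illustrate scale and are not estimates for this trial. The remedy costs little, so it is worth adopting even if the smaller effect is the true one.

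**What to change.** - **Section 7, counting.** Date a TLT by onset. Any qualifying toxicity that begins on or before day 28 counts toward the 3-of-10 rule when its 7- or 14-day clock runs out, even if that is after day 28.
- **Section 7, pause.** Keep accrual paused until every such open event among the first 10 treated patients has been classified. For the last patient this is day 42 at the latest.
- **Section 7, follow-up.** State that AE follow-up of an open event continues when a patient's cycle 2 is held. Section 6.1 holds therapy for grade 3 non-hematologic and grade 4 hematologic toxicity, so the scheduled cycle 2 visits may be deferred and cannot be relied on alone.
- **Section 14.1.** Make the suspension sentence match section 7. With all first-cycle-onset TLTs counted, the existing table stands unchanged.

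Patient-level treatment rules do not change. The cost is wording, at most 14 more days of pause and only if an event is open at day 28, and possibly an AE contact for a patient whose cycle 2 is on hold.

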### **8. ADVERSE EVENTS: LIST AND REPORTING REQUIREMENTS**

Adverse event (AE) monitoring and reporting is a routine part of every clinical trial. The following list of reported and/or potential AEs (Section 7.1) and the characteristics of an observed AE (Section 7.2) will determine whether the event requires expedited reporting **in addition** to routine reporting.

